20	APPENDICES	61
20.1	APPENDIX I	61
20.2	APPENDIX II	62
20.3	APPENDIX III	63
20.4	APPENDIX IV	64
21	SUMMARY OF SIGNIFICANT CHANGES TO THE PROTOCOL	68

LIST OF ABBREVIATIONS

5hmC	5-hydroxymethylcytosine
95% CI	95% Confidence Interval
AE	Adverse Event
BCT	Blood Collection Tube
BMI	Body Mass Index
cfDNA	Cell-free DNA
CAP	College of American Pathologists
CI	Chief Investigator
CPSP	Clinical Performance Study Protocol
CTIMP	Clinical Trials of Investigational Medicinal Products
CNV	Copy Number Variation
CRF	Case Report Form
CT	Computerized Tomography
DICOM	Digital Imaging and Communication in Medicine
DM	Diabetes Mellitus
IDMC	Independent Data Monitoring Committee
DMP	Data Management Plan
DNA	Deoxyribonucleic acid
EHR	Electronic Health Record
GCP	Good Clinical Practice
GP	General Practitioner
HbA1c	Haemoglobin A1c
HPB	Hepatobiliary
ICF	Informed Consent Form
IPMN	Intraductal Papillary Mucinous Neoplasm
ISF	Investigator Site File
IVD	In Vitro Diagnostic Device
MCN	Mucinous cystic neoplasms
MDT	Multidisciplinary Team
MDST	Multidisciplinary Study Team
MHRA	Medicines and Healthcare products Regulatory Agency
MRCP	Magnetic Resonance Cholangiopancreatography
MRI	Magnetic Resonance Imaging
NIHR RRDN	National Institute of Health and Care Regional Research Delivery Network
NOD	New Onset Diabetes
NPV	Negative Predictive Value
PanIN	Pancreatic Intraepithelial Neoplasia
PC	Pancreatic Cancer
PIC	Participant Identification Centre
PID	Patient Identifiable Data
PIS	Participant Information Sheet
PPV	Positive Predictive Value
PV	Portal Vein
QNS	Quantity Not Sufficient
RDC	Rapid Diagnostic Centre
REC	Research Ethics Committee
SAE	Serious Adverse Event
SAP	Statistical Analysis Plan
SCTU	Southampton Clinical Trials Unit
SDSC	Specialist Diabetes Service Centres

SEER	Surveillance, Epidemiology and End Results
SIV	Site Initiation Visit
SMA	Superior Mesenteric Artery
SMV	Superior Mesenteric Vein
SoC	Standard of Care
STAI	6-item Spielberger State Trait Anxiety Inventory
TMF	Trial Master File
TMG	Trial Management Group
TMP	Trial Monitoring Plan
TSC	Trial Steering Committee
QNS	Quantity Not Sufficient

KEYWORDS

Diabetes Mellitus, Early detection, Pancreatic Cancer, HbA1c, Epigenomics, 5hmC

CLINICAL PERFORMANCE STUDY SYNOPSIS

Short title	SAFE-D
Full title:	S urveillance of p A ncreatic health a F ter diabEtes D iagnosis

Population:	Up to 15,000 male and female participants between the age of 50-84 years with newly diagnosed type II diabetes mellitus (within previous six months) across the UK.
Primary Objective:	
 • Pilot - evaluation of recruitment feasibility. 
If successful, this will be followed by two study stages involving cumulative participant recruitment:
 
 • Study stage 1 – interim analysis of co-primaries sensitivity and specificity of Avantect test for pancreatic cancer, pancreatic cancer resectability rate • Study stage 2 – final analysis of co-primaries sensitivity and specificity of Avantect test for pancreatic cancer, pancreatic cancer resectability rate
Secondary Objective:	
 • To evaluate the Avantect test in detecting pancreatic cancer across the pilot, study stage 1 and study stage 2 combined in terms of: 
 ○ Pancreatic cancer stage shift ○ Positive predictive value (PPV) ○ Negative predictive value (NPV) ○ Actual pancreatic cancer resectability rate • To evaluate the beneficial effect of the Avantect test in terms of: 
 ○ Overall survival (time-to-event) ○ Time to pancreatic cancer diagnosis relative to new onset diabetes (NOD) diagnosis ○ Effect on state anxiety over time ○ Performance characteristics for high-grade neoplasia
Rationale	Pancreatic cancer is one of the most lethal common cancer (five-year survival 5-7%). Early detection and treatment could significantly improve overall survival. It is known that people who develop new type II diabetes are at higher-than-average risk for harbouring occult pancreatic cancer and there is currently no accepted clinical strategy for their surveillance. The Avantect pancreatic cancer test is intended for the qualitative detection of the presence or absence of an abnormal 5-hydroxymethylcytosine (5hmC)-based epigenomic and genomic signature in plasma cell-free DNA (cfDNA) derived from peripheral whole blood collected in a Streck® blood collection tube. The Avantect test may aid in

[figure not shown]
	identifying occult pancreatic cancer in patients with new onset type II diabetes who are 50 – 84 years old and, following additional diagnostic imaging, could enable earlier treatment for pancreatic cancer which may increase survival rates.
Clinical Performance Study Design:	Prospective, single blinded interventional randomised multicentre study
Sample size:	Up to 15,000 participants across the UK in the following stages: 
 • Pilot: target 800 participants • Study stage 1: up to an additional 5,600 participants • Study stage 2: up to an additional 8,600 participants There will be a data driven ‘stop-go’ decision at the end of each stage before progressing to the next stage.
Treatment/Intervention:	Participants will be blindly randomised into two arms; 
 • Intervention arm: Avantect test performed within prioritised time frame with intent to share only “detected” test results with the participants and their General Practitioners (GPs) in parallel to making a referral to the local secondary care clinical team for further investigations. All test results will be included in primary endpoint analysis. • Control arm (Standard of Care [SoC] arm): Participants will receive the current standard of care for diabetes management. Samples will be used for potential future Avantect testing and/or future research.
Number of specimens required per participant:	Three peripheral blood samples per participant (up to 30 mL in total) will be collected at three timepoints
Duration of the clinical performance study:	Participant involvement on trial: 3 visits over 12 months Length of remote follow-up collection for each participant: 36 months from consent Recruitment duration: 36 months Total study duration (including 12m analysis and report writing): 7 years

URL for Database:	https://www.imedidata.com
URL for randomisation:	https://www.imedidata.com

Primary Study Endpoints:	Pilot: Recruitment rate Study stage 1 & 2: Sensitivity and specificity of Avantect test for detecting pancreatic cancer, pancreatic cancer resectability rate
---------------------------------	--

Secondary Study Endpoints:	Secondary endpoints (pilot and study stage 1 and 2 combined) will include pancreatic cancer stage shift, PPV, NPV and proportion of pancreatic cancer patients undergoing surgical resection
Exploratory Endpoints	Overall survival (time-to-event) Time to pancreatic cancer diagnosis (NOD to pancreatic cancer diagnosis) 6-item Spielberger State Trait Anxiety Inventory (STAI) Performance characteristics for high-grade neoplasia
Total Number of Sites:	Up to 3,000 GP practices and up to 200 Specialist Diabetes Service Centres

TRIAL SCHEMA

1. INTRODUCTION

1.1 JUSTIFICATION FOR THE DESIGN OF THE CLINICAL PERFORMANCE STUDY

There is currently no accepted screening test for pancreatic cancer in average risk individuals (i.e., those without a known risk factor such as a constitutional mutation, multiple first-degree relatives with pancreatic cancer, or a pre-existing pancreatic cystic disease). Furthermore, among people who are known to have higher risk, no secondary, or risk-based screening test or procedure is widely accepted. Although it is known that people older than 50 years who develop type II diabetes mellitus (DM) are at higher-than-average risk for harbouring occult pancreatic cancer¹⁻⁴, there is currently no accepted clinical strategy for testing new onset diabetes (NOD) patients for the presence of pancreatic cancer (PC).

1.2 RATIONALE (INCL. RISK-TO-BENEFIT) FOR IVD MEDICAL DEVICE UNDER INVESTIGATION

Research⁵ shows that 5-hydroxymethylation changes in plasma-derived cell-free DNA (cfDNA) can be used for early detection of PC. 5-hydroxymethylcytosine (5hmC) is a stable epigenetic mark that arises as the first step of active demethylation of methylated-cytosine base in DNA by ten-eleven translocation enzymes, marking regions of active transcription and gene regulation⁶. Based on the technology developed⁶, the Avantect blood-based test utilises 5hmC, fragmentation and copy number variation (CNV)-based biomarkers from cfDNA whose measures are associated with the detection of PC. The test employs state-of-the-art machine learning stacked ensemble modelling that combines multiple feature sets to predict the presence of PC using 5hmC-based epigenomic and genomic signatures in cfDNA. The ensemble model was trained and rigorously tested using 25 iterations of 10-fold outer cross validation. Specifically, for each fold in the outer folds, a model was trained on the in-fold data using further 10-fold cross validation and tested on the remaining out-of-fold data. The model parameters and classification score threshold was optimised during inner fold training. A classification score threshold that represented the 98% specificity in the training set was chosen. The model was validated in an independent cohort of 2,150 participants of which 2,048 were non-cancers and 102 with PC. The performance of PC detection was at 66.7% sensitivity and 96.9% specificity with an early-stage PC (Stage I and II) sensitivity of 68.3%.

ClearNote Health feasibility data also suggests that the Avantect test may detect a subset of neoplastic cysts, including intraductal papillary mucinous neoplasms (IPMNs) and pancreatic intraepithelial neoplasms (PanINs). IPMNs of the pancreas and PanINs are PC precursors. Just as colon polyps can develop into colon cancer if left untreated, some IPMNs have the potential to become malignant, so it is important to diagnose and manage them early and appropriately before they develop into an invasive cancer.

The ClearNote Health Avantect pancreatic cancer test is intended for the qualitative detection, in NOD individuals, of the presence or absence of an abnormal 5hmC-based epigenomic and genomic signature in plasma cfDNA derived from peripheral whole blood collected in a Streck® blood collection tube (BCT). The Avantect test aids in identifying occult PC in patients with NOD who are 50 years old or older. These patients can then benefit from additional diagnostic imaging to rule out PC.

People with NOD, an expanding subset of the UK population (about 240,000 patients diagnosed every year in England, according to the 2021 National Diabetes Audit)⁷, are at increased risk for harbouring occult PC. Current standard of care fails to detect these cancers until it is too late. Avantect holds the promise of identifying people with NOD for whom further investigations may yield early detection of PC for a more successful intervention. Given existing clinical evidence that individuals with NOD have been linked to a higher incidence of PC, this study is designed to evaluate a novel non-invasive epigenomics-based test to detect pancreatic cancer early and improve resection rate. With the use of such a non-invasive test the risk to the participants is negligible, however if proven to detect PC earlier, this could have significant survival benefits for both the trial participants and future newly diagnosed diabetes mellitus patients.

Pancreatic cancer is a Cancer Research UK area of unmet need with 5-year survival rates as low as 5%⁸. Other blood-based cancer detection studies are underway, such as Pathfinder, SYMPLIFY⁹, and NHS-Galleri¹⁰, but these studies are evaluating multi-cancer detection tests. There are ongoing observational studies in PC detection, such as UK-EDI¹¹ but the SAFE-D study is a randomised single blinded interventional study in patients with newly diagnosed diabetes mellitus who are at a higher-than-average risk of developing PC.

1.3 BENEFITS AND RISKS OF THE IVD MEDICAL DEVICE UNDER INVESTIGATION AND CLINICAL PERFORMANCE STUDY

1.3.1 Risks and anticipated adverse device effects

ClearNote Health has established requirements for managing product risks associated with the development and commercialisation of Avantect. Risks have been graded based on severity (grade 1-5, where 1 indicates negligible and 5 indicates catastrophic) probability of occurrence (grade 1-5, where 1 indicates an improbable and 5 a frequent occurrence) and detectability (grade 1-5, where 1 indicates certainty of detection and 5 undetectable). Hazard analysis identified risks associated with collection of blood to be minimal (more details in Adverse Events section 8). With respect to the Avantect test itself, the primary risk relates to a false assay result (i.e., a false positive or a false negative result). All

Avantect “detected” cases will require an MRI (CT-scan only if MRI is contraindicated). Rare adverse events associated with MRI are described in Adverse Event Section 8.

Risks associated with the clinical performance study have been assessed in the SAFE-D Trial Risk Assessment.

2. CLINICAL PERFORMANCE STUDY OBJECTIVES AND ENDPOINTS

2.1 PRIMARY STUDY OBJECTIVES

The study will be divided into a pilot and two stages:

- Pilot: The goal of the six-month pilot is to determine if the enrolment strategy (identifying eligible subjects via commercial recruitment platforms, NIHR Research Delivery Network Primary Care Networks and Specialist Diabetes Service Centres (SDSC)) is adequate, and to identify barriers and develop mitigation strategies to improve recruitment. Participants may also self-refer to the study following viewing study information found on the study website or displayed in Primary Care locations. The pilot will also assess the BMI distribution to determine whether body mass index (BMI) should be included as eligibility criteria in study stage 1 and 2. We will aim to open up to 450 Participant Identification Centres (PICs) during the pilot and at least 30 recruitment hubs where participants can attend for study visits (also referred to as sites).
- The pilot will be considered successful if:
 - Recruitment rate is greater than 10% of invitation to enrolment, or
 - 800 participants are enrolled, or
 - Enrolment is greater than an average of 133 participants per month in the last three months of pilot
- The feasibility of continuation to study stage 1 and 2 will be assessed by the Trial Steering Committee based on recruitment during the pilot
- Study stage 1 will enrol an additional 5,600 NOD participants with the primary objective to evaluate sensitivity and specificity of the Avantect test in detecting pancreatic cancer in 3,200 intervention arm participants with 1 year of follow-up for futility and efficacy.
- Study stage 2 will enrol an additional 8,600 participants to make a total of 15,000 NOD participants with the primary objectives of evaluating sensitivity and specificity of the Avantect test in detecting pancreatic cancer in intervention arm participants, and comparing the proportion of pancreatic cancers deemed resectable across the intervention and control arms.

2.2 PRIMARY ENDPOINTS:

- Pilot: Recruitment rate - number of NOD individuals enrolled into the study divided by the number of individuals invited to participate.
 - Recruitment rate to be greater than 10% of invitation to enrolment OR
 - 800 participants are enrolled OR
 - Enrolment is greater than an average of 133 patients per month in the last 3 months of the pilot.
- Study stage 1 and 2:
 - Sensitivity of Avantect test for detecting PC – number of individuals in the intervention arm with one or more Avantect “detected” test results and PC divided by the number of individuals in the intervention arm with PC.
 - Specificity of Avantect test for ruling out PC – number of individuals in the intervention arm with no Avantect “detected” test results, at least one Avantect “not detected” test result and no diagnosis of PC divided by the number of individuals in the intervention arm with no diagnosis of PC.
 - Resectability rate – number of individuals with PC deemed resectable by the study multidisciplinary team (MDT) divided by the number of PCs.

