2.4 TABLE OF ENDPOINTS/OUTCOMES PILOT

	Objective	Outcome Measures	Summary method(s)
Primary	To determine the recruitment rate	Recruitment rate	
 Percentage recruited of all participants invited Number of individuals recruited per month

STUDY STAGE 1 and 2 (analysis inclusive of pilot):

	Objective	Outcome Measures	Summary method(s)
Primary	To estimate the proportion of PCs deemed resectable	Resectability rate	Percentage of PCs deemed resectable by the study MDT [compared between arms]
	To estimate the sensitivity of the Avantect test in detecting PC	Sensitivity	Percentage with PC diagnosed who have an Avantect “detected” result [within intervention arm]
	To estimate the specificity of the Avantect test in ruling out PC	Specificity	Percentage without PC diagnosed who have one or more Avantect “not detected” results and no Avantect “detected” results [within intervention arm]
Secondary	To determine the effect of the Avantect test on PC stage shift	Stage shift	Percentage of PCs diagnosed at stage I/II [compared between arms]
	To estimate the PPV of Avantect for detecting PC	PPV	Percentage with an Avantect “detected” result who have PC diagnosed [within intervention arm]

	To estimate the NPV of Avantect for ruling out PC	NPV	Percentage of individuals with no Avantect “detected” test results who have no diagnosis of PC [within intervention arm]
	To estimate the proportion of PCs that are resected	Resection	Percentage with PC who underwent resection [compared between arms]
Exploratory	To estimate the time from NOD diagnosis to PC diagnosis	Time to diagnosis	Kaplan-Meier curve Hazard ratio [within intervention arm]
	To estimate the overall survival of study participants	Overall Survival	Kaplan-Meier curve Hazard ratio [compared between arms]
	Assess the effect of the Avantect test on state anxiety over time	6-item STAI	T-test or non-parametric alternative if suitable [compared between arms]
	To investigate the performance characteristics for high-grade neoplasia	Sensitivity Specificity PPV NPV	As described above, but disease positive is defined as PC and/or high-grade mucinous cysts and non-cases defined as no pancreatic cancer or high-grade mucinous cysts. This will be repeated where high-grade mucinous cysts are considered as disease positive and PCs are excluded. [within intervention arm]

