Participants may also self-refer to the study following viewing study information found on the study website, on social media or displayed in Primary Care locations. Interested subjects can book their T0 appointment at a conveniently located recruitment hub (specified local GP practice or other appropriate locations) via the website or call a member of the clinical study team at the hub for more information and help to book the appointment.

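### The pilot recruitment rate divides all enrolments, including self-referrals who were never invited, by invitations, so it is not the invitation-to-enrolment conversion that its 10% criterion describes

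*Protocol*

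**What the plan says.** Section 2.2 of the protocol defines the pilot recruitment rate as the "number of NOD individuals enrolled into the study divided by the number of individuals invited to participate". The table in section 2.4 summarises the same endpoint as "Percentage recruited of all participants invited", together with a monthly recruitment count.

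Section 2.1 lists three criteria, any one of which makes the pilot a success. The first is worded "Recruitment rate is greater than 10% of invitation to enrolment, or". The second is a total of 800 enrolments. The third is a mean above 133 enrolments a month across the pilot's final three months.

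The purpose is given in the same section: "The goal of the six-month pilot is to determine if the enrolment strategy (identifying eligible subjects via commercial recruitment platforms". The bracket goes on to name research-network primary care and the specialist diabetes centres. The next sentence opens a further route: "Participants may also self-refer to the study following viewing study information found on the study website or displayed in Primary Care locations". Section 5.1 repeats this route through the booking website, and section 7.2 adds social media.

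Two other statements fix who is counted. Section 5.1 treats everyone who signs the consent form as enrolled, whatever the route. Sections 7.2 and 7.3 describe invitation as contact with, or an approach to, people identified from GP or diabetes-centre records.

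**The concern.** A conversion rate needs a numerator drawn from its denominator. Here the numerator is everyone enrolled and the denominator is everyone invited, and the protocol describes a route by which a person can enrol without an invitation. Nothing in sections 2.2 or 2.4 removes such people from the numerator or says how to treat someone who was invited and then booked independently.

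Two quantities are thus attached to one primary endpoint. The formula in section 2.2, followed literally, gives total enrolments per invitation. The wording of the 10% criterion and of section 2.4 points to the share of invited people who enrol.

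The difference matters because the criteria are alternatives, so the ratio can satisfy the success rule unaided. Section 5.1 also gives the pilot the task of estimating how many sites are needed, and a yield that mixes two sources is harder to use for that.

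**Working it through.** **Inputs from the protocol.** Pilot target 800 in six months; recruitment-rate threshold above 10%; monthly threshold above 133 over the last three months (sections 2.1 and 2.2).

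**Input not in the protocol.** The share s of pilot enrolments that were never invited. I assume 5% to 30% to show the range.

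**Reproducing the plan's own figure.** 800 / 6 = 133.3 per month, which matches the stated 133. The 10% threshold is set, not derived, so there is nothing to reproduce.

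**Relation between the two rates.** Let E be all enrolments and I all invitations.

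- Stated ratio: R = E / I
- Uptake among the invited: u = E(1 − s) / I = R(1 − s)
- So R = u / (1 − s), and R exceeds 10% whenever u exceeds 10% × (1 − s)

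| Assumed never-invited share s | Invited uptake at which R reaches 10% |
|---|---|
| 5% | 9.5% |
| 10% | 9.0% |
| 15% | 8.5% |
| 20% | 8.0% |
| 30% | 7.0% |

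**Example with assumed counts.** Take 600 enrolled and 5,800 invited.

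- Stated ratio: 600 / 5,800 = 10.3%, so the criterion is met.
- If 15% were never invited, 600 × 0.85 = 510 invited people enrolled.
- Invited uptake: 510 / 5,800 = 8.8%, which is below 10%.
- At s = 5% the invited uptake would be 570 / 5,800 = 9.8%; at s = 30% it would be 420 / 5,800 = 7.2%.

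**Does this change the verdict?** Only if both other criteria fail. With 600 enrolled, the 800 criterion fails. The monthly criterion fails if the last three months total 3 × 133 = 399 or fewer. Even enrolment would give 300 in three months, so it would fail. If enrolment rises late and 400 or more of the 600 join in that period, the pilot succeeds on the monthly criterion and the definition of the rate makes no difference to the verdict.

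**The case against.** The strongest reply is that a sensible reading is already in the text. The criterion speaks of conversion from invitation to enrolment and section 2.4 of a percentage of those invited, so a careful analyst would count invited people only. That reading is reasonable, and it is the one the fix adopts. It does not remove the problem, because section 2.2 gives an explicit formula with an unrestricted numerator. The protocol fixes both formula and threshold, so this is not detail left to the SAP.

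Several other points stand and limit the importance:

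- The share s is unknown. At 5% the shift from 10% to 9.5% is trivial.
- Not every self-referrer is uninvited. Someone who sees a poster at a participating practice may also have received an invitation and would properly count in the numerator.
- The Trial Steering Committee assesses the feasibility of continuing on the pilot's recruitment, and section 2.4 reports monthly numbers as well.
- The T0 data lists in sections 7.1 and 7.6.1 name no entry-route item. The Data Management Plan is not at hand, so it cannot be said that the route goes unrecorded.

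A reader might go further and infer that later stages would need more invitations than the pilot rate suggests, by the factor 1/(1 − s): about 1.05 at s = 5% and 1.43 at s = 30%. The documents do not support this as a general conclusion. The full factor applies only if self-referral supplies none of the later 5,600 + 8,600 = 14,200 participants. Sections 5.1 and 7.2 describe self-referral as a route into the study as a whole. If it continues in the same proportion to invitations, total enrolments per invitation is the right planning ratio.

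A reader might also infer that the pilot will be wrongly declared a success. Nothing in the protocol shows that; it requires a material s and failure of both other criteria.

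**Conclusion.** The point holds in a limited form. As written in section 2.2, the pilot's primary endpoint is not a proportion of invited people and does not match the conversion that its own criterion and section 2.4 describe. Followed literally, the 10% criterion can be met with invited uptake below 10%: at 9.5% if 5% of enrolments were never invited, and at 7.0% if 30% were. Those shares are assumptions.

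The verdict on the pilot depends on the definition only when enrolment is under 800, the last three months average 133 or fewer per month, and invited uptake lies between 10% × (1 − s) and 10%. Even then the Trial Steering Committee's assessment follows. Sensitivity, specificity, resectability and the main sample size are untouched. This is a defect in the definition of a feasibility endpoint. It is worth correcting because it is cheap, but it is no threat to the main results.

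**What to change.** - In sections 2.2 and 2.4, define the recruitment rate as invited individuals who enrol divided by individuals invited. State that a person who was invited and then booked by self-referral counts in the numerator.
- Record entry route and invitation status at T0.
- Report self-referred enrolment separately, per month and as a share of all enrolments, so that the committee sees what each source yields.
- Keep total enrolment, self-referrals included, for the 800-enrolled and 133-per-month criteria, which measure overall capacity and are sound as they are.
- If pilot yield is used to project invitations or sites, state the assumption about whether self-referral grows with invitations.

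The cost is a wording change in two sections and, if not already collected, one or two data items at T0. Eligibility, randomisation and participant care do not change. The downside is that the reported recruitment rate may be slightly lower.
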